### **Phase 2: Open Trial (Enrollment COMPLETE)**

We will conduct an open trial to obtain pilot data. In the open trial, we will enroll 16 patients with assessments at pre-, post-, 1-month, and 3-month follow-ups to pilot the measures we expect to use in the RCT. At the end of the 1st iteration ( $n=4$ ), the PI will compare actual data to target feasibility and acceptability outcomes. Deviations from target outcomes will prompt investigation and discussion with the research team and advisory board, and possible revision of the intervention or research procedures. We will repeat this process in 3 more iterations of 4 patients. The open trial will inform the design of the RCT.

This is a sub-study under the existing protocol entitled "Establishing the Effectiveness of Cognitive-Behavioral Partial Hospitalization for Anxiety, Depression, and Overall Functioning" (# 2010-P-001047/6). Data obtained under the existing BHP protocol will be shared with Investigators from this study.

### **Procedures under existing BHP protocol:**

This research will be conducted with each patient who enters our program (up to 900 adult patients each year). As the Behavioral Health Partial Program is an adult CBT-based program, all patients are at least 18 years of age and up. Upon registration in our program, patients will receive the Mini-International Neuropsychiatric Interview (M.I.N.I.), a 20-45 minute non-invasive, structured diagnostic psychiatric interview to assess for psychiatric diagnostic criteria. Patients will also be asked to complete a self-report questionnaire assessing for demographic variables, symptom severity, functional impairment, and CBT skill acquisition upon registration, and upon

discharge. Information will be stored on-site, in a locked drawer, in a secure office. Patients' original questionnaires will be maintained for no longer than five years. Only the Principal Investigator ([name]), Research Coordinator, Nurse Director ([name]), and Program Director ([name]) will have access to PHI. However, the majority of PHI will be stored electronically. The proposed research will be using RedCap Database, an encrypted, electronic database that is both HIPPA compliant (Health Insurance Portability and Accountability Act) and approved by Partners IRB for the administration and storage of human subject information (for additional information on the RedCap Database feature see <http://rc.partners.org>). To minimize inconvenience and provide maximum benefit to patients, data collection will be streamlined as a part of standard clinical care. Clinically salient information, including diagnostic output and patient's self report scores, will be highlighted and presented to clinical team managers and others involved in patient services. Non-BHP patients will not be able to participate in this research.

#### **Procedures for Proposed Protocol:**

Participants' data collected as part of protocol (# 2010-P-001047/6) will be used to determine eligibility for this study, and to characterize the demographic and clinical characteristics of the sample and as outcome assessments. Thus, only participants who consent to the main BHP study protocol will be eligible for the current study.

On patients' second day at the BHP, staff will offer participation. Interested patients will complete the eligibility assessment. Study staff will immediately review scores on the measure of interpretation bias (WSAP; see Measures) to determine eligibility. If eligible, they will complete the remaining pre-assessment measures. If ineligible, patients will be compensated and continue with treatment as usual at the BHP,

The partial hospital employs a bachelor's level progress monitoring coordinator who collects self-report data from patients and transmits this information to treatment teams. Identical to the pilot study, the PI will train this person to orient patients to HabitWorks and reinforce the rationale and instructions provided in the videos embedded within the app. The staff member will also conduct brief, in-person "check-ins" as often as desired by the patient, to answer questions about the intervention, provide accountability for the patient, and to provide encouragement. This extra support and human connection with the HabitWorks program should ensure adherence during the acute phase of treatment. On occasions when the progress monitoring coordinator is unavailable, a member of the study staff may provide the orientation and check-ins.

Participants will complete a task designed to improve interpretation biases. Each session includes 150 trials of the previously validated word-sentence association paradigm during each session (~10 min). The task presents ambiguous sentences ("You failed an exam") and provides positive feedback ("you are correct!") when participants endorse benign interpretations/attributions ("difficult test") and negative feedback ("you are incorrect!") for negative interpretations/attributions ("stupid").

Once enrolled, participants will complete HabitWorks daily on their smart phones in a quiet room while attending the partial hospital, three times per week at home for 1-month following discharge, and as desired during the final 2 months. Sessions during the follow-up period will include approximately 75 trials and thus will only require 5 minutes to complete.

During the 1-month post-acute period, participants will complete assessments of symptoms (PHQ-9 and GAD-7) as often as desired, including optional once weekly check-ins and daily assessment of affect (see EMA description in Measures). These surveys will be administered

via Metricwire. The Metricwire app was designed to protect participants' privacy, confidentiality, and data security. Only research personnel will have access to study information. Data collected by the Metricwire app is encrypted, and downloaded by the researcher to the local research server in a de-identified format (i.e., subject ID number). The local research server is only accessible by study staff. Study staff will provide orientation to the app and answer any questions regarding the assessments and data collected.

Treatment phase	Location	Frequency of sessions	Session duration
Acute (1 to 14 days)	Hospital	Daily to augment CBT-based hospital treatment	10 min
Transition (1-month)	Home	3x per week to transition from intensive hospital to outpatient care	5 min
Long-Term (2 mo)	Home	Sessions completed as desired by individual	5 min

Following Long-Term phase (post 3months from discharge) EPIC Research trained study staff will check every patients EMR, whether or not they completed the 3month assessment, for data on rehospitalization or ER visits and the reason why. This data will then be de-identified and kept in partners secure storage (Dropbox).

**Retention.** Post-discharge, staff will monitor participants' progress with the HabitWorks app daily and will call participants who have not completed any sessions in the past week. The purpose of these phone calls will be to help identify barriers and brainstorm potential solutions. To increase retention, we will: a) obtain contact information of individuals who will always know how to reach participants; b) pay participants for assessments; and c) provide transportation if needed, flexible scheduling for the assessments, and in rare individual cases conduct interviews via telephone.

### Measures.

Participants will complete measures that are already administered as part of standard clinical care at the BHP.

The Mini International Neuropsychiatric Interview (MINI) is a structured interview assessing for DSM-V Axis I disorders. The MINI will be administered by doctoral practicum students and interns in clinical psychology who will receive weekly supervision by the post-doctoral fellow.

The PHQ-9 is a brief self-report questionnaire assessing symptoms of depression. Patients complete the PHQ-9 at daily.

The GAD-7 is a brief self-report questionnaire assessing symptoms of anxiety. Patients complete the GAD-7 daily.

The Quality of Life Enjoyment and Satisfaction Questionnaire (Q-LES-Q) will assess satisfaction and quality of life.

To assess suicidal ideation and behaviors (lifetime, past month), we will use the interview administered *Columbia Suicide Severity Rating Scale* (CSSRS). During remote assessments, when clinical interview is not possible, we will use an adapted form of the CSSRS as a self report measure.

Participants in proposed study will complete the following additional measures:

WSAP. Word-sentence pairs representing benign or negative interpretations are presented, and patients decide if they are related or not. In the assessment version of this task, no feedback is given about the accuracy of participants' responses. The task will record reaction times for 4 WSAP trial types (endorse benign, reject benign, endorse negative, reject negative), reflecting the relative speed or ease with which participants make interpretations. We will

calculate reaction time bias scores for each trial type (negative vs. benign). The task will also record participants' responses (yes/no) for each trial type (negative vs. benign) to allow calculation of the percentage of negative and benign interpretations endorsed. In the case of remote recruitment in phase 2b and 3, the assessment version of the WSAP will be used as a screening tool prior to the Pre-treatment.

Schedule of Assessments	Pre	Daily	Post	1-mo	3-mo
Interviews					
MINI	X				
CGIS			X	X	X
WSAS	X		X	X	X
Longitudinal Interval Follow-Up Eval				X	X
Qualitative Exit Interview (open trial and first 20 in RCT)				X	
CSSRS	X			X	X
App or Computer Delivered					
*The HabitWorks app will deliver all daily surveys. Redcap will be used to deliver computerized surveys during in-person assessments.					
Demog. Form, CEQ	X				
PHQ-9; GAD-7	X	X	X	X	X
Q-LES-Q, BHS, CFI, MPS, GSE	X		X	X	X
Exit Questionnaire				X	
WSAP	X	X	X	X	X
Scenario Recognition Task				X	
EMA PANAS	X	X	X	X	X
CSSRS- Self Report	X			X	X
System Usability Scale- HW condition				X	
TWEETS- HW condition				X	

The Scenario recognition task is the most widely used assessment of interpretation bias in CBM- and will ensure that effects are not solely attributable to practice or method effects. In brief, participants first read 10 ambiguous scenarios and a comprehension question to ensure they actually read the scenario. In the second phase, participants read the title of the ambiguous scenario followed by four versions of the final sentence presented in a random order. Sentences represent a) a possible positive interpretation, b) a possible negative interpretation, c) a positive foil, and d) a negative foil.

Participants rate each sentence for its similarity in meaning to the original story using a 4-point scale ranging from 1 (very different in meaning) to 4 (very similar in meaning). We will calculate the average similarity rating for negative and positive interpretations.

Co-primary clinical outcomes will include stake-holder relevant measures of global improvement and functioning. The PI will train study staff to administer these brief scales and will monitor reliability using established procedures at the BHP.

Clinician-administered Clinical Global Improvement Scale (CGIS) to assess global improvement.

Clinician-rated 5-item Work and Social Adjustment Scale (WSAS) to assess interference caused by the patient's symptoms in the domains of work, home management, leisure, and family relationships.

Other self-report measures will include:

Credibility Expectancy Questionnaire to assess patients' beliefs about the treatment expectancy (affectively based) and treatment rationale credibility (cognitively based).

Exit Questionnaire to assess patients' satisfaction with the treatment provided.

Beck Hopelessness Scale (BHS) to assess negative attitudes about the future.

Cognitive Flexibility Inventory: The Cognitive Flexibility Inventory is a measure of mental flexibility and assesses the degree to which individuals are able to replace maladaptive thoughts with adaptive ones and maintain a balanced mindset.

15-Item Multidimensional Perfectionism Scale (short form): The MPS is a widely used self-report measure of perfectionism.

10-item General Self Efficacy Scale: The GSE is a widely used self-report measure of self efficacy.

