### BACKGROUND AND SIGNIFICANCE

There is an urgent unmet treatment need for individuals with Serious Mental Illness (SMI). NIMH Strategic Objective 4 states that the “chronic disability and *early mortality of Serious Mental Illnesses (SMI)...*demand a rapid response.” Over 4% of the adult US population has a SMI, defined as a mental disorder associated with significant functional impairment. SMI spans diagnostic categories, including individuals with a range of mood and anxiety disorders, among others. Individuals with SMI die 10-32 years prematurely, and are almost 13 times more likely to die by suicide. Hospitalization is common among those with SMI, with 9% estimated to have received inpatient care in 2014, not including partial hospital and residential levels of care. Hospital stays are typically brief, and residual symptoms upon discharge predict relapse and re-hospitalization. Moreover, hospitalized patients often exhibit residual cognitive and functional impairments, despite symptom improvement. The months following discharge from hospitalization are risky, as individuals transition from a highly structured and supportive environment to home, acute stressors, and uncertain aftercare. Interventions that efficiently accelerate improvement are urgently needed to reduce residual symptoms upon discharge and ultimately risk of rehospitalization. Ideally, augmentation strategies need to be reliably and easily delivered both in the hospital and continued during the transition to outpatient care.

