**Aim 3 : Obtain pilot data on CBM's effect on suicidal ideation and behaviors.**

## **III. SUBJECT SELECTION**

### **Phase 1: Development (COMPLETED)**

In this first phase of this R34 pilot effectiveness trial, there will be no human subjects. The PI will meet with various stakeholders (e.g., clinicians at study site, clinic directors, BHP Patient Advisory Board) to obtain feedback about the HabitWorks app and research procedures.

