### Measures:

All measures from the Open Trial will remain the same. Additionally, the RCT will include the following new measures:

Edinburgh Handedness Inventory- Short Form^116 is a 4-item widely used validated measure of handedness. The EHI will be used to determine eligibility for the EEG Assessment. Participants rate how often they use their left or right hand in 4 different practical examples on a scale of +100 ("Always Right") to -100 ("Always Left"). We will consider a score of +50 or above as right handed and eligible for EEG.

The System Usability Scale(SUS): The SUS is a 10-item assessment of the usability of a given product or service, and was intended to be used for all types of technological interventions. It collects the subjective self-report of usability and specifically relates to user experience of effectiveness, efficiency, and satisfaction. Participants will rate their agreement on a 5point likert scale ranging from 1(Strongly Disagree) to 5(Strongly Agree). This survey will be administered at the 1-Month Assessment, only for individuals in the HabitWorks condition.

The Twente Engagement with Ehealth Technologies Scale (TWEETS): The TWEETS is a 9-item self-report measure used to assess user engagement with health apps. It will be used to assess the level of cognitive, affective, and behavioral engagement that participants have with the HabitWorks app. Participants will rate their agreement on a 4point likert scale ranging from 0(strongly disagree) to 4(strongly agree). This survey will be administered at the 1-Month Assessment, only for individuals in the HabitWorks condition.

Study staff will conduct a qualitative exit interview for the first 20 participants regarding questions similar to the Open Trial, but pertinent to either Symptom Tracking or HabitWorks treatment conditions. Additionally participants will be asked about their experience in relation to the EMA in transition phase.

Finally, the Symptom Tracking condition will receive a different version of the Exit Questionnaire and the Credibility and Expectancy Questionnaire.

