#### ***Suicidality***

As part of standard clinical care, the PMC will monitor suicidal ideation daily, via use of item 9 on the PHQ-9 using RedCap. As part of standard clinical care, the PMC will notify the clinical team manager of any patient whose experiences an increase from the baseline assessment (e.g., from a 0 to 1, from a 1 to 2, etc.). At that point, the treatment team will manage the safety of the patient and determine whether inpatient hospitalization is required. Each time item 9 on the PHQ-9 increases by one or more points, the PMC will again notify the clinical team manager of the symptom increase.

As part of standard clinical care, patients complete the Columbia Suicide Severity Rating Scale upon admission to the BHP. As part of this study, they will also complete it at post-BHP treatment. Answers of "Yes" to questions 4 or 5 on C-SSRS will result in emergent evaluation by licensed clinician (either BHP clinical team manager or [name]). During periods where the BHP is operating remotely, participants will complete the self-report version of the C-SSRS during study assessments. In these instances, study staff will monitor their responses in real-time, and will ensure that a licensed clinician is available at time of study assessment for emergent evaluation if necessary (Answers of "Yes" to questions 4 or 5).

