### ***Suicidality***

As part of this study, participants will complete the Columbia Suicide Severity Rating Scale at 1 and 3-month follow-up assessments. Answers of "Yes" to questions 4 or 5 on C-SSRS will result in emergent evaluation by licensed clinician member of study staff ([name]) for appropriate assessment and triage (see risk assessment section below). In addition to clinical interview, as well as when clinical interview cannot be scheduled, participants will complete a self-report version of the C-SSRS. When this occurs, study staff will monitor their responses in real-time, and will ensure that a licensed clinician is available remotely at time of study assessment for emergent evaluation if necessary (Answers of "Yes" to questions 4 or 5). If [name] is unavailable to conduct a risk assessment another pre-determined licensed clinical psychologist will reach evaluate the patient. If multiple risk assessments are required for the same participant, we will attempt to have the same clinician speak with the patient at all risk assessment timepoints

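### As written, the C-SSRS recall frames leave roughly the second month after discharge outside any past-month window, so recurrences in that month without hospital contact cannot be told from earlier history.

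*Protocol*

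**What the plan says.** Aim 3 in the Protocol's Specific Aims is to "Obtain pilot data on CBM's effect on suicidal ideation and behaviors". The C-SSRS is the instrument for it. Under Measures in the open-trial part of V. Study Procedures, the text reads "To assess suicidal ideation and behaviors (lifetime, past month), we will use the interview administered" C-SSRS, with an adapted self-report form when an interview is not possible. No other recall frame appears in either document.

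The Schedule of Assessments marks the interview and the self-report form at Pre, 1 month and 3 months. The Lab SOP agrees for the period after discharge: "participants will complete the Columbia Suicide Severity Rating Scale at 1 and 3-month follow-up assessments". For the end of the partial hospital stay the SOP adds "As part of this study, they will also complete it at post-BHP treatment", which the schedule does not mark under Post. The Phase 3 Measures section carries the set into the randomised trial: "All measures from the Open Trial will remain the same". Phase 3 also makes the 1- and 3-month assessments optional.

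After month 3, staff check each patient's medical record, whether or not the 3-month visit took place, "for data on rehospitalization or ER visits and the reason why". The SAP's Phase 3 section plans between-group effect sizes with 95% confidence intervals and gives no scoring or analysis rule for the C-SSRS.

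**The concern.** A one-month look-back at visits two months apart does not cover the whole interval. The lifetime frame does span it, but a lifetime answer that is already positive stays positive whether or not anything new happens. The missing stretch lies in a period of which the Background says "The months following discharge from hospitalization are risky".

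What is at stake is the completeness of Aim 3's pilot data. If suicidal ideation or behaviour over the three months after discharge is to be reported by arm, recurrences in about a third of that time would be lost unless they led to hospital contact. The losses would fall on participants with a previous history. That group may be large here, because Phase 3 drops the open trial's exclusion based on PHQ-9 item 9.

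**Working it through.** The plan states no figure on this point, so there is none to reproduce. The check is a count of days followed by a comparison of answer patterns.

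**Inputs.** The recall frames are lifetime and past month (Protocol, Measures). The visits are at 1 and 3 months after discharge (Schedule of Assessments; Lab SOP). I assume visits on days 30 and 90 and a month of m = 30 days, and then vary these.

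**Coverage.** A past-month item asked on day v covers days v - m + 1 to v.

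- 1-month visit: 30 - 30 + 1 = 1, so days 1-30.
- 3-month visit: 90 - 30 + 1 = 61, so days 61-90.
- Uncovered: days 31-60, which is 30 of 90 days = 33%.

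**Sensitivity.**

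- m = 28: the 3-month window is days 63-90, so the gap after the 1-month visit is days 31-62, or 32 days.
- m = 31: the 3-month window is days 60-90, so the gap is days 31-59, or 29 days.
- 3-month visit held on day 104 (m = 30): the window is days 75-104, so the gap is days 31-74, or 44 days.
- 1-month visit missed (m = 30): only days 61-90 are covered, so 60 of 90 days = 67% are not.

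The extra administration in the SOP falls at discharge and looks back from there, so it adds nothing for days 31-60.

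**What the lifetime item adds.** Take one C-SSRS item answered yes or no at both visits. The documents describe no event count or date.

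| Lifetime, 1 month | Lifetime, 3 months | Past month, 3 months | What is known about days 31-60 |
|---|---|---|---|
| No | Yes | No | A first-ever event occurred, and it falls in this period |
| No | Yes | Yes | A first-ever event occurred after the 1-month visit; months 2 and 3 cannot be separated |
| Yes | Yes | No | Nothing: the answers are the same with or without a recurrence |
| Yes | Yes | Yes | Nothing beyond an event in month 3 |

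The loss is therefore confined to the last two rows, where the participant was already positive on that item.

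**Other sources for days 31-60.** The record check finds events that led to rehospitalisation or an ER visit. It is described under the open trial, and I take it to apply to both arms of Phase 3. The LIFE interview is described as covering psychiatric medication use and changes. Weekly surveys in months 2 and 3 are voluntary, are described for the Symptom Tracking arm, and are not monitored by staff. None of these reliably records a recurrence without hospital contact.

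**The case against.** The best reply is that the recall frames come from a one-line description, under a list of measures already used in routine care. The Lab SOP says the routine C-SSRS is given on admission, where lifetime and past month fit naturally. Neither document shows the form used at 1 or 3 months or the wording of the adapted self-report. This stands: the gap follows from the text as written and is not shown to exist in the forms. If another version is used at follow-up, the Protocol should say so.

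A second reply is that Aim 3 only seeks pilot data, that past-month status at 1 and 3 months is a coherent outcome, and that the windows are the same in both arms. This also stands. Past-month status at each visit is not invalid; only occurrence over the whole follow-up is incomplete.

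Three stronger readings are tempting, and the documents do not support them.

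- **That nothing new in the second month can be detected or dated.** The first two rows of the table show that first-ever events are detected and sometimes placed in that month, and the record check finds events with hospital contact.
- **That the pilot's 70% at moderate or high suicide risk gives the share who would set off the question 4/5 trigger on history alone.** That figure is a MINI category from a different sample, not C-SSRS answers, and attendance at follow-up is optional.
- **That events in the second month escape a safety net that a longer recall period would restore.** The trigger works only at an assessment, so a longer frame would bring later capture, not earlier protection. The Protocol states openly that surveys between visits are not monitored, and it relies on safety plans, crisis lists and app messages.

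**Conclusion.** The point holds in a limited form. Followed as written, the C-SSRS frames leave about 30 of 90 post-discharge days outside any past-month window, or about 60 of 90 if the 1-month visit is missed. Within that time, a recurrence that led to no rehospitalisation or ER visit cannot be separated from earlier history in a participant already positive on the item. The documents do not allow an estimate of how many events this affects.

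The conclusion assumes that the stated frames apply at follow-up, that visits fall near days 30 and 90, and that a month means 28 to 31 days. It calls for an inexpensive improvement to the Aim 3 data and does not undermine the trial.

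One inconsistency stands apart from the gap. The Lab SOP calls for evaluation after a positive answer to question 4 or 5 without naming a time frame, while the Measures section gives the instrument two.

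**What to change.** At every post-baseline administration, interview and self-report alike, keep the past-month item and add one covering the period since the last completed assessment. Derive Aim 3's post-discharge occurrence outcome from the added item, and say so in the SAP. Replacing the past-month item would be worse: comparability with Pre would be lost, and the 1- and 3-month windows would differ in length.

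If both visits are completed, the uncovered time after the 1-month visit falls from about 30 days to none. If only the 3-month visit is completed, the added item still covers the whole period. If the 3-month visit is missed, the change does not help.

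The cost is one more recall question per administration, a line each in the Protocol and SAP, and a recall period of about two months at the 3-month visit (about three if the 1-month visit was missed). No new visit or staff is needed.

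Two passages need reconciling by the investigators alongside this. The SOP's C-SSRS at the end of the partial hospital stay is not in the Schedule of Assessments. If it is not given, the first follow-up item reaches back to Pre and takes in the hospital stay as well. The question 4/5 trigger must also be reconciled with the instrument's time frames, including any frame added here.
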